### *ROC Analysis*

The amount of surfactant dose received (1st dose only) is potentially a key determinant of whether or not an infant requires mechanical ventilation within 4 days of birth. A ROC analysis will be undertaken to explore the ability of dose received to discriminate between those infants who do and those infants who do not require mechanical ventilation over this time period. The ROC analysis plots sensitivity against 1-specificity with points on the ROC curve (AUC) determined by varying the cut-off for dose received. Providing the AUC is greater than 0.7 an optimal cut-off for discrimination purposes will be chosen using Youden's J statistic. A one-sided p-value assessing whether the AUC is significantly greater than 0.5 will also be calculated.

The FiO2 level at the point of decision to administer surfactant is potentially a key determinant of CPAP failure resulting in the requirement for mechanical ventilation within 72 hours of birth. A ROC analysis will be undertaken to explore the ability of FiO2 level to discriminate between those infants who fail on non-invasive methods of ventilation and those infants who do not require mechanical ventilation over this time period. The ROC analysis plots sensitivity against 1-specificity with points on the ROC curve (AUC) determined by varying the cut-off for dose received. Providing the AUC is greater than 0.7 an optimal cut-off for discrimination purposes will be chosen using Youden's J statistic. A one-sided p-value assessing whether the AUC is significantly greater than 0.5 will also be calculated.

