## NNRD Fields

Surfactant can be administered prophylactically (usually within the delivery room) or as rescue (usually within the neonatal ward). If surfactant is given prophylactically, it is assumed that this is the first administration.

If administered prophylactically, it is proposed that the following data items are added under the 'NNUEpisodes-Labour & Delivery' category within the electronic record:

	Question	Answer
1	Volume of surfactant administered in millilitres (mL)	[free text box]
2	Method of surfactant administration	
 
• Endotracheal tube
 
• INSURE (endotracheal tube in place for 15 minutes or less)
 
• Thin catheter for minimally invasive/less invasive surfactant administration
 
• Other
 

3	Time of initial surfactant administration	[free text]
4	Specify any analgesics and/or sedatives used for surfactant administration (drug and dose)	[free text]

Surfactant can also be administered in a rescue setting, usually within the neonatal unit. In this setting, the frequency of administration is captured (i.e. whether this is the infant's first, second or third dose). The following fields are proposed under the 'Respiratory-Daily' category:

	Question	Answer
1	Volume of surfactant administered in first dose, millilitres (mL)	[free text box]
2	Specify the method of surfactant administration	
 
• Endotracheal tube
 
• INSURE (endotracheal tube in place for 15 minutes or less)
 
• Thin catheter for minimally invasive/less invasive surfactant administration
 
• Other
 

3	How many doses of surfactant were administered today?	[Free text box]
4	Time of initial surfactant administration	[free text]
5	Specify any analgesics and/or sedatives used for surfactant administration (drug and dose)	[free text]
6	FiO 2 at point of decision to administer surfactant	
 
• < 30 %
 
• 30- 39 %
 
• 40 - 49 %
 
• 50 - 59 %
 
• ≥ 60 %
 

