## 4. Study Population

### a. Number of Participants

*Proposed sample size: 1300*

The study is powered based on assumed proportions requiring mechanical ventilation within 72 hours of 60% and 45% in the dosing groups 100-130 mg/kg and 170-200 mg/kg respectively. The required power is 80% with the treatment comparison being undertaken at the two-sided 5% level of significance. At the planning stage the proportions of patients falling into the two dosing groups is not known. The sample size for the propensity score matched analysis is determined by the smaller of the two dosing groups and also the ability to find a match for each infant in that group. The table below provides total sample sizes required based on the assumptions set down according to various splits for the proportions of infants in the two dosing groups. Note also that the assumption has also been made that 10% of infants will receive a dose that falls between the upper limit of the lower dose group and the lower limit of the higher dose group. We will also assume that for 25% of infants in the smaller dosing group a match cannot be found. Sample sizes for 90% power are provided for completeness.

The proposed initial sample size of 1300 covers a range of possible assumptions regarding the split across the dosing groups including 45%/45%, 40%/50% and 35%/55%. An interim evaluation of the proportions of infants who fall into the two dosing groups will be undertaken on the first 400 infants recruited into the study to provide a check of the assumed breakdown and a sample size change considered if these assumptions are not correct.

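### The FiO2 ROC is written as a dose ROC over a different time window, and the dose ROC states no direction and uses an AUC threshold its own planning rates would not reach

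*Protocol*

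**What the plan says.** Protocol section 6, ROC Analysis, has two paragraphs.

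- **Dose paragraph.** It asks how well first dose separates infants who do and do not need mechanical ventilation within 4 days of birth.
- **FiO2 paragraph.** It asks the same of FiO2 at the decision to give surfactant, among infants managed non-invasively, but for ventilation within 72 hours of birth.
- **Both paragraphs.** Each describes the curve as having "points on the ROC curve (AUC) determined by varying the cut-off for dose received". Each then says "Providing the AUC is greater than 0.7 an optimal cut-off for discrimination purposes will be chosen" by Youden's J, and adds a one-sided p-value for AUC above 0.5. Neither states which direction of the marker counts as positive, and neither states any covariate adjustment.

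Elsewhere in the protocol:

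- The exploratory objectives pair FiO2 with ventilation within four days, and the primary endpoint is also four days.
- NNRD Fields lists FiO2 "at point of decision to administer surfactant" as a new item with five answers: below 30%, 30-39%, 40-49%, 50-59%, and 60% or more. It is in the rescue list only. The prophylactic list has no FiO2 item.
- Section 4a plans on "assumed proportions requiring mechanical ventilation within 72 hours of 60% and 45% in the dosing groups 100-130 mg/kg and 170-200 mg/kg respectively". The sample size table adds a 60% vs 40% row.
- Comparative fields says that dose is calculated from the volume given and birth weight.

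**The concern.** A ROC for FiO2 has to move the FiO2 cut-off. The paragraph moves dose instead, so followed literally it gives a second dose ROC and leaves the FiO2 question unanswered. It would also do so on a time window that the FiO2 objective does not use.

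For dose, the matter is how the result will be read. A group difference worth powering a study on can still correspond to weak discrimination between individual infants. If the planning effect puts the AUC far below 0.7, the Youden step will almost never be reached, and a reader may take that as evidence against a dose effect. If the analyst uses the common software convention that a higher marker value predicts the event, a true benefit of higher dose puts the AUC below 0.5, and the one-sided test looks in the wrong tail.

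Lastly, mg/kg dose has birth weight in its denominator, and the rationale section says whole-vial dosing is common. The primary analysis adjusts for birth weight and gestational age; the ROC as described does not.

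**Working it through.** **1. FiO2 definition and window, side by side.**

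| Item | Dose ROC | FiO2 ROC | FiO2 objective | Primary endpoint |
|---|---|---|---|---|
| Marker named | first dose | FiO2 | FiO2 | – |
| Cut-off varied | dose | dose | – | – |
| Window | 4 days | 72 hours | 4 days | 4 days |

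The description of the curve is the same in both paragraphs, so the FiO2 paragraph contradicts its own aim.

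**2. FiO2 bands.** Five ordered bands have four boundaries: 30, 40, 50 and 60%. A ROC on them is valid but can examine only those thresholds. The loss in AUC is small. In a binormal simulation, a continuous AUC of 0.70 becomes 0.690 with equal band shares and 0.685 with shares of 10/35/30/15/10%. The binormal form and the shares are assumptions. No expected FiO2 AUC can be derived from the protocol.

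**3. The plan's own figure.** The protocol states no expected AUC. The rates used below can be checked against the sample size table: (1.960 + 0.842)² × (0.60×0.40 + 0.45×0.55)/0.15² gives 171 per group after rounding up, and 2 × 171/(0.75 × 0.45) = 1013.3, against 1014 in the table. The leading factor of 2 is needed for the match and is not in the stated rule; that is a separate matter and does not affect the AUC.

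**4. Dose AUC, two equal groups, lower dose positive.**

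- 60% vs 45%: sensitivity = 0.60/(0.60 + 0.45) = 0.571; specificity = 0.55/(0.55 + 0.40) = 0.579; AUC = (0.571 + 0.579)/2 = 0.575.
- 60% vs 40%: sensitivity 0.60, specificity 0.60, AUC 0.60.
- With higher dose as positive, 60% vs 45% gives 1 − 0.575 = 0.425.

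**5. Other dose distributions.** The model is log-odds of ventilation linear in dose, matched to the planning rates of the two groups. Within 100-200 mg/kg, 10% of doses lie between the groups.

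| Setting | 60% vs 45% | 60% vs 40% |
|---|---|---|
| Two groups, splits 45/45 to 35/55 | 0.571-0.575 | 0.595-0.600 |
| Continuous dose within 100-200 mg/kg | 0.581-0.583 | 0.607-0.611 |
| 10-30% of doses outside 100-200 mg/kg (assumed) | 0.595-0.622 | 0.626-0.660 |
| Doses spread evenly over 60-260 mg/kg (assumed) | 0.64 | 0.68 |

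The protocol gives no figure for doses outside 100-200 mg/kg, although its MHRA reporting section allows for them.

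**6. Effect needed for an AUC of 0.7.** Keep the two rates averaging 52.5%. For two groups, 72.5% vs 32.5% gives 0.725/1.05 − 0.275/0.95 = 0.401, and 0.5 + 0.401/2 = 0.70. That is a difference of about 40 points. For continuous dose within 100-200 mg/kg it is about 36 points. The planning difference is 15.

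**7. Precision at 1300 infants.** The Hanley-McNeil formula is SE² = [A(1−A) + (n₁−1)(u−A²) + (n₀−1)(v−A²)]/(n₁n₀), with u = A/(2−A) and v = 2A²/(1+A). Put in A = 0.575, n₁ = 682 (52.5% of 1300) and n₀ = 618. Then u = 0.4035, v = 0.4198, A² = 0.3306 and SE = 0.0158.

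- Distance to the 0.7 threshold: (0.7 − 0.575)/0.0158 = 7.9 standard errors.
- Test of AUC above 0.5, lower dose positive, one-sided 5%: 0.075/0.0158 = 4.75 standard errors, power above 99%.
- Same test, higher dose positive: the estimate lies 4.75 standard errors on the wrong side.

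**The case against.** The strongest reply is that this is an exploratory analysis whose intent is clear. The FiO2 paragraph names FiO2 as the marker, so a competent statistician would probably vary FiO2. Orienting the marker is routine and may be in the analysis plan, which is not shown. Declining to choose a cut-off when discrimination is weak is a sensible safeguard. The dose effect itself is tested by the matched comparison, not by the ROC. Much of this stands, and it limits the point. It does not rescue a stated rule that names the wrong variable, or a window that differs from the objective. The 72 hours may echo the CPAP-failure definition in the Introduction, but the protocol does not say so.

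A reader might infer four stronger things that the protocol does not support.

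- **That the section cannot deliver the cut-offs it promises.** The cut-off is conditional on the AUC, and the AUC and its p-value are calculated in any case.
- **That banded FiO2 invalidates the ROC.** Ordered bands give a valid curve and a Youden choice among four thresholds.
- **That a dose cut-off would mainly reflect birth weight.** Confounding is plausible, but no figure in the protocol shows its size.
- **That the 0.7 threshold is certain to be missed.** The 60% and 45% were set for the matched comparison, whereas the ROC states no matching or adjustment. Confounding could move the observed AUC either way.

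**Conclusion.** The point holds in a limited form. The FiO2 ROC is wrong as written on the variable it moves and inconsistent with its objective on the window; neither finding rests on an assumption.

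For dose, the protocol's main planning rates imply an AUC of 0.57-0.58, and the 60% vs 40% row implies 0.60-0.61. Wider dose spreads raise this to at most 0.68 in the settings examined. A Youden dose cut-off is thus very unlikely even if the hypothesis is true. This rests on applying the matched-comparison rates to the ROC, on a log-odds trend linear in dose for the continuous settings, and on assumed dose spreads beyond 100-200 mg/kg. Weak discrimination and a real 15-point group difference are compatible, so missing 0.7 says little about whether dose has an effect.

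The missing direction matters because the one-sided test has over 99% power one way and points away from the hypothesised effect the other way. Confounding by birth weight is a possibility to address, not a demonstrated bias. The wording should be corrected; the primary comparison is not affected.

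**What to change.** 1. **FiO2 ROC.** State that the curve is formed by varying the FiO2 cut-off, in infants on non-invasive support when the decision to give surfactant is made. Align the window with the four-day endpoint.
2. **FiO2 field.** Record FiO2 as a number, since the field is being created for this study, or state that only 30, 40, 50 and 60% can be examined. Note also that the listed field covers rescue treatment only.
3. **Dose direction.** State that lower dose is the positive direction for the one-sided test.
4. **Reading the threshold.** Add a sentence that the planning rates imply an AUC well below 0.7, and that failing the threshold is not evidence of no dose effect.
5. **Adjustment.** Supplement the dose ROC with a logistic dose-response model, for example a spline in first dose, with the covariates of the primary analysis. Report predicted ventilation probability across dose with confidence bands.

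The cost is protocol wording, one field format if FiO2 becomes numeric, and a little more analysis work. The sample size and the primary analysis are unchanged.

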### *Analysis of secondary and exploratory objectives*

Statistical analysis will also be carried out on secondary and exploratory endpoints.

## 7. MHRA reporting

Chiesi Limited is legally obliged to all report off-license use of any of its products to the MHRA. Any off-license use of Curosurf which is identified as part of the analysis of the raw data will be collated by the Chiesi pharmacovigilance team and reported to the MHRA. This includes the following:

- Dose of Curosurf used outside the licensed dose (100 – 200 mg/kg)
- Curosurf administered to treat RDS in a baby < 700g
- Curosurf administered prophylactically in a baby < 24 weeks or > 31 weeks gestational age

As only anonymised data will be analysed as part of this study, only aggregate data will be reported, and there will be no further follow-up to identify further information.

## 8. Good Clinical Practice

The research will be conducted in accordance with Good Clinical Practice, the Association of the British Pharmaceutical Industry (ABPI) Code of Practice, and the Data Protection Act.

Data extracted from the NNRD for the purposes of this protocol is anonymised. No patient identifiable data will be shared with any party, including the sponsoring pharmaceutical company, Chiesi Limited.

## 9. Research Conduct Responsibilities

### a. Protocol Amendments

The Chief Investigator will seek approval from Chiesi Limited for any amendments to the protocol or other associated documentation, and vice versa. Amendments to the protocol or other associated documentation will not be implemented without approval from Chiesi Limited and if necessary from the REC and NHS Trust R&D Office.

### b. End of Research

The end of the research is defined as the extraction of the two year data for the final patient recruited. Chiesi Limited has the right to terminate the research for any reason.

## 10. Reporting and Publication of Results

The study will be registered on the ISRCTN registry.

An independent statistician will analyse the NNRD data set against the pre-agreed analysis plan.

### **The effect of surfactant dose on outcomes in preterm infants with RDS**

The results of the research will be made publicly available either in the form of a conference abstract/poster presentation, or submitted as a publication in a peer-reviewed journal within one year of study closure.

The decision to publish will be jointly taken between Chiesi and all the Investigators. The authors on any publication(s) will be based on the ICMJE authorship guidelines.

The final data set will be available to other researchers within three years of study end.

## 12. Appendix A

Category	Category Detail	Item Name	Field ID	NHS data Dictionary Item Name	Format/Length	Coding/allowed values	Description	Purpose
NNUEpisodes	Demographics and Birth Information (Baby)	Birth weight (g)	Birthweight	BIRTHWEIGHT	N4	Accepted range is between 001-9998g...9999 Unknown	Birth weight at the time of delivery in grams	Used to identify risk factors on admission to neonatal care
NNUEpisodes	Demographics and Birth Information (Baby)	Sex of the baby (phenotypic)	SexPhenotype	PERSON PHENOTYPIC SEX	N1	1 Male 2 Female 9 Indeterminate/Intersex	The sex of the baby. 'Not known' is an option if information is missing or not recorded. 'Not specified' is an option for instances where the sex cannot be determined at birth.	Used to aggregate data by sex
NNUEpisodes	Demographics and Birth Information (Baby)	Gestation age in weeks	GestationsWeeks	GESTATION LENGTH (AT DELIVERY)	N2	10-49	The best obstetric estimate at the time of delivery in weeks. This will normally be based on the postmenstrual age but, if appropriate, may be modified on the basis of antenatal ultrasound. Where gestation at delivery is not known, this is based on the postnatal estimate of maturity	Used to identify risk factors on admission to neonatal care

## The effect of surfactant dose on outcomes in preterm infants with RDS

NNUEEpisodes	Antenatal (Pregnancy details)	Were steroids given during pregnancy?	Steroids Antenatal Given	STEROIDS GIVEN DURING PREGNANCY TO MATURE FETAL LUNGS INDICATOR	an 1	Derived N No Y Yes 9 Unknown	Administration of any dose of steroid to mother (dexamethasone or betamethasone), at any time during pregnancy, with the intention of maturing foetal lungs.	Used to compare outcomes for babies
NNUEEpisodes	Antenatal (Pregnancy details)	Number of antenatal steroid courses given	Steroids Antenatal Courses	ANTENATAL STEROID COURSE COMPLETION STATUS CODE	n1	1 - Complete: A full course of steroids at any time during pregnancy 2 - Incomplete: At least one injection of steroids given at any time during pregnancy 3 - Not Given 9 - Unknown	A complete course of steroids is defined by the RCOG guideline as two 12mg doses of betamethasone, given intramuscularly, 24 hours apart. Some units may use another regimen, including a different steroid. A complete course is one which complies with the local protocol.	Used to compare outcomes for babies
NNUEEpisodes	Labour & delivery	Methods of resuscitation	Methods OfResuscitation	NEONATAL RESUSCITATION METHOD (NATIONAL NEONATAL DATA SET)	an 3	00 None 10 Stimulation 11 Positioning managing airways 12 Oxygen 13 Suction 14 Bag and face mask IPPV 15 Intubation 16 Cardiac massage	Interventions used during resuscitation or stabilisation immediately after delivery of the baby.	Used to monitor neonatal outcomes

## The effect of surfactant dose on outcomes in preterm infants with RDS

NNUEpisodes	Labour & delivery	Drugs used during resuscitation	DrugsForResuscitation	NEONATAL RESUSCITATION DRUG (SNOMED CT DM+D)	n18	dm+d code for any drug	If medication was administered at resuscitation please select relevant medications.	Used to monitor neonatal outcomes
NNUEpisodes	Labour & delivery	Was surfactant given during resuscitation?	SurfactantGivenResuscitation	SURFACTANT GIVEN INDICATOR (DURING RESUSCITATION)	an1	N No Y Yes 9 Unknown	Surfactant given during resuscitation	Used to monitor neonatal outcomes
NNUEpisodes	Discharge details	Discharge date and time	DischDateTime	CRITICAL CARE DISCHARGE DATE AND TIME	an19	DateTime coding (e.g. 1997-07-16T19:20:30) Date (an10 CCYY-MM-DD) Time (an8 HH:MM:SS)	The date and time, Coordinated Universal Time (UTC), on which an inpatient completes this episode of care, either because of death, transfer to another ward or hospital, or because of discharge home.	Used to measure length of stay and to calculate the anonymised version of this field
NNUEpisodes	Discharge details	Date of death and time	DateofDeath	PERSON DEATH DATE AND TIME (DURING NEONATAL CRITICAL CARE PERIOD)	an19	DateTime coding (e.g. 1997-07-16T19:20:30) Date (an10 CCYY-MM-DD) Time (an8 HH:MM:SS)	The date and time, Coordinated Universal Time (UTC), on which an inpatient had died in this episode of care as stated on the death certificate. If the discharge destination indicates the infant died this item is required	Used in survival analyses and calculate anonymised dates

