### a. Comparative fields

In order to investigate whether surfactant dose affects neonatal outcomes, the following data will be obtained from the NNRDs:

	NNRD field	Purpose of using this field for this study
1	Demographics > Birth weight	Using this field alongside the volume of surfactant used, the dose of surfactant will be calculated.
2	Demographics > Sex of the baby (phenotypic)	Characterisation of cohort
3	Demographics > Gestation weeks and day	Inclusion/exclusion criteria
4	Antenatal > Were steroids given during pregnancy?	Characterisation of cohort
5	Antenatal > Number of antenatal steroid courses given	Characterisation of cohort
6	Labour & delivery > Methods of resuscitation	Characterisation of cohort
7	Labour & delivery > Drugs used during resuscitation	Characterisation of cohort
8	Labour & delivery > Was surfactant given during resuscitation?	Characterisation of cohort
9	Respiratory > Respiration: Surfactant given today	Inclusion/exclusion criteria
10	Discharge details > Discharge time and date (anonymised)	Duration of hospitalisation, age at discharge
11	Discharge details > Date of death and time - anonymised	Calculation of mortality
12	Discharge details > cause of death	Determination of outcomes
13	Discharge details > Discharge oxygen	To investigate whether the dose of surfactants can affect whether infants are discharged on oxygen.
14	Respiratory > Respiratory support device and support mode (daily)	To investigate whether using there is a correlation between surfactant dose and respiratory device
16	Discharge details > Clinical diagnoses at discharge	To correlate the dose of surfactant, and/or method of surfactant administration is related to clinical diagnoses at discharge
17	Retinopathy of prematurity > ROP stage*	To determine whether the dose of surfactant is related to the severity of retinopathy of prematurity
18	Cranial ultrasound scan > IVH**	To determine whether the dose of surfactant is related to the severity of periventricular haemorrhage

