**The effect of surfactant dose on outcomes in preterm infants with RDS**

19	Medication > Drugs given on this day	To identify infants who have received surfactant during their hospitalisation period, and which surfactant To identify which infants received analgesics or sedatives on the same day as surfactant, and which babies were given postnatal steroids
20	Two year follow up > Respiratory & CVS system – On supplemental oxygen or any respiratory support?	To determine whether the dose of surfactant is related to whether the infants requires supplemental oxygen at 2 years
21	Two year follow up > Development – at 24 month corrected age***	To determine whether the dose of surfactant is related to infant development (normal or mild, moderate or severe delay).
22	Two year follow up > Bayley III cognitive, total raw score	To determine whether the dose of surfactant is related to the infant's cognitive ability

\*There are two NNRD fields for this outcome (right and left eye)

\*\*There are two NNRD fields for this outcome (right and left side)

\*\*\*There are four NNRD fields for this outcome (normal and mild, moderate or severe delay)

The full list of NNRD fields can be found in Appendix A.

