**The effect of surfactant dose on outcomes in preterm infants with RDS**

NNUEpisodes	Discharge details	Cause of death	Cause of death	DEATH CAUSE ICD CODE (DURING NEONATAL CRITICAL CARE PERIOD)	an 6	ICD-10	Specify the major reasons for death of the baby from the list of International Classification of Diseases (ICD) as corresponding with death certificate.	Used to compare outcomes for babies
NNUEpisodes	Discharge details	Discharge:: Oxygen	Discharge Oxygen	RECEIVING OXYGEN THERAPY ON DISCHARGE INDICATOR	N	Delivered from Daily Data Item N No Y Yes	Item specifies if the baby is receiving and is dependant on oxygen therapy on discharge home.	Used to compare outcomes for babies.
NNUEpisodes	Discharge details	Clinical diagnoses at discharge	DiagnosesAtDischarge	DIAGNOSIS (ICD RECORDED ON DISCHARGE FROM NEONATAL CRITICAL CARE) and/or DIAGNOSIS (SNOMED CT ON DISCHARGE FROM NEONATAL CRITICAL CARE)	an 16/n18	ICD-10 and/or SNOMED CT Can be derived from daily records	Specify all the applicable diagnoses for this baby if not already recorded in the daily diagnoses	Used to monitor infant care, evaluate health status and outcomes
Daily	Respiratory	Respiration: Respiratory support device	Respiratory support	RESPIRATORY SUPPORT MODE (NATIONAL NEONATAL DATA SET)	N1	1 Endotracheal tube2 Tracheostomy3 Nasal cannula4 Nasopharyngeal cannula5 Face mask	Type of respiratory support device any time during the 24 hour period (00.00-23.59)	Used to determine level of care
Daily	Respiratory	Respiration: Surfactant given today	DaySurfactantGiven	SURFACTANT GIVEN INDICATOR (ON NEONATAL CRITICAL CARE DAILY CARE DATE)	an 1	N No Y Yes	Records if baby received any dose of surfactant in this day while in the neonatal unit. Surfactant given at delivery/resuscitation is a data	Used to determine health status of infant

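### The requested discharge date also marks transfers, and no discharge destination is requested, so an infant whose last neonatal episode ends in transfer out of neonatal care cannot be told from one who went home

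*Protocol*

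**What the plan says.** Protocol section 3a (Comparative fields) requests the discharge date and time for this purpose: "Duration of hospitalisation, age at discharge". Appendix A defines that item as the time at which an episode of care ends, "either because of death, transfer to another ward or hospital, or because of discharge home", and gives its general use as "Used to measure length of stay and to calculate the anonymised version of this field".

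Section 3a also requests discharge oxygen: "To investigate whether the dose of surfactants can affect whether infants are discharged on oxygen". Appendix A describes it this way: "Item specifies if the baby is receiving and is dependant on oxygen therapy on discharge home". It is filed as an episode-level item, its coding column says that it comes from a daily data item, and its only values are yes and no.

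The source data hold a discharge destination, because the Appendix A entry for date of death relies on it: "If the discharge destination indicates the infant died this item is required". Neither section 3a nor Appendix A requests it. Section 3a closes with "The full list of NNRD fields can be found in Appendix A".

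Oxygen at discharge home and duration of respiratory support are secondary endpoints (section 2b). Length of stay and age at discharge are not endpoints at any level; they appear only as the purpose of a field.

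**The concern.** A date that can mean death, transfer or going home is used as if it meant one thing, and the field that would say which is not requested. Infants in neonatal care are moved between units and to other wards, and the protocol expects some movement: section 6 puts inborn status in the propensity model.

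Two secondary endpoints depend on knowing how neonatal care ended. Oxygen at discharge home needs to know who went home from the recorded episode. Duration of respiratory support needs to know whether support had stopped or only the record had.

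The error need not be equal in the two dose groups. Under the whole-vial dosing described in section 2b, the dose per kilogram depends on the infant's weight, and transfer plausibly depends on size and illness as well. Section 5 says that the original data are destroyed after the final analysis, so a field left out of the request may not be recoverable later.

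**Working it through.** No figure in the protocol can be reproduced here, so the check sets the field definitions side by side. Section 3 says that the database covers every NHS neonatal unit admission in England, Scotland and Wales. For each way a recorded episode can end, the requested fields show the following.

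| Ending of the episode | Discharge date | Date of death | Later neonatal episode | Distinguishable from discharge home? |
|---|---|---|---|---|
| Discharge home | yes | no | none expected | reference |
| Death | yes | yes | none | yes |
| Transfer to another covered neonatal unit | yes | no | yes | yes, if episodes are joined |
| Transfer to a setting outside the database | yes | no | none | no |

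The third row depends on a joining rule, which the protocol does not state. The fourth row cannot be resolved by any rule applied to the listed fields.

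Consequences by outcome:

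- **Length of stay and age at discharge.** Both stop at the transfer date for infants in the fourth row, and also for those in the third row if episodes are not joined.
- **Duration of respiratory support.** This comes from the daily respiratory records, not from the discharge date. Those records cover days in neonatal care. An infant who leaves for a non-neonatal ward while still on support has a censored duration that looks complete.
- **Oxygen at discharge home.** The definition refers to going home, but the item has only yes and no codes and comes from daily data. Its value for an episode that ends in transfer is not specified.
- **Mechanical ventilation within four days of birth.** This does not use the discharge date and is little affected.

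The size can be shown only under assumptions. Let *h* be the true share on oxygen at discharge home, *u* the share of infants whose transfer goes undetected, and *q* the share of those coded yes for discharge oxygen. Then

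recorded share = (1 − u)h + uq, and error = u(q − h).

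Assume h = 15%, equal in transferred and other infants. Take two cases for q: 50% (assumed), if the item carries oxygen status on the day of transfer, and 0%, if every transfer is coded no.

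| u (assumed) | q = 50% | q = 0% |
|---|---|---|
| 0% | 15.0% | 15.0% |
| 10% | 0.90 × 0.15 + 0.10 × 0.50 = 18.5% | 0.90 × 0.15 = 13.5% |
| 30% | 0.70 × 0.15 + 0.30 × 0.50 = 25.5% | 0.70 × 0.15 = 10.5% |
| 50% | 0.50 × 0.15 + 0.50 × 0.50 = 32.5% | 0.50 × 0.15 = 7.5% |

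If u were 30% in one dose group and 20% in the other, the false difference would be 0.10 × (0.50 − 0.15) = +3.5 percentage points in the first case and 0.10 × (0 − 0.15) = −1.5 points in the second. None of these inputs is in the protocol. The table shows that the error could go in either direction, and that it vanishes when no transfer goes undetected. It does not estimate the error.

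**The case against.** A reader might infer that every transferred infant is counted as discharged, that respiratory follow-up stops at the first transfer, and that home oxygen is wrong for all of them. The protocol does not support this. Appendix A closes an episode, not an infant's record. The database covers receiving neonatal units as well, so a transfer between units should leave a further episode. Respiratory support is read from daily records. Discharge oxygen is defined by reference to going home, which matches the endpoint. Nothing says that only the first episode is extracted.

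Joining records is also implicit in the design. Episode, daily and two-year follow-up items have to be combined for each infant, which needs some infant-level key. The exclusion of patient identifiers in section 5 does not rule out a pseudonymous one. A rule for joining episodes is ordinary analysis-plan detail, and section 10 refers to a pre-agreed analysis plan that is not available here.

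These arguments stand, and they remove most of the stronger reading. They do not reach the missing field. An analysis plan cannot use a destination that was not extracted, and joining episodes does not help where no later episode exists. One could reply that the list may not be literally complete, since inborn status has no row of its own in either list although section 6 uses it. That is a reason to check the request, not to assume that discharge destination is in it.

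**Conclusion.** The point holds in a limited form. From the fields listed, an infant whose last neonatal episode ends in transfer to a setting outside the database cannot be distinguished from one discharged home. Length of stay and age at discharge may be truncated for these infants. The secondary endpoints of oxygen at discharge home and duration of respiratory support may be misclassified, or treated as complete when they are censored. Transfers between covered neonatal units add to this only if episodes are not joined, which the protocol leaves open.

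The primary comparison is little affected. The size of the error on the secondary endpoints is unknown: the protocol gives no transfer rate, no oxygen rate and no coding rule for transfers. The conclusion rests on taking Appendix A at its word as the full list. If discharge destination is in fact extracted, only the wording needs correcting.

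**What to change.** - Add discharge destination to section 3a and Appendix A.
- State that final discharge is taken from the last of each infant's neonatal episodes, joined by a pseudonymous key.
- Count oxygen at discharge home only where the destination is home, and report how many infants left neonatal care by another route.
- Treat transfer out of neonatal care as censoring for duration of respiratory support.
- Ask the data provider what value discharge oxygen takes when an episode ends in transfer, and record the answer.

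The cost is one existing field in the data request, a small amount of derivation work and a wording change. Sites have nothing further to collect. The request should be settled before the data are extracted.
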